Analytic Datasets	The analytic dataset will comprise all patients enrolled, where enrollment is defined when the FlowTriever System enters the patient's vasculature or the patient is diagnosed with PE and the primary treatment strategy of anticoagulation is administered (Conservative Therapy Sub-study) and the patient provides consent to share his/her personal health information.

Follow-up Schedule	
Patients will have follow-up evaluations after the index procedure* at:
 
 • 48 hours (\pm 36 hours) • 30 days (\pm 15 days) • 6 months (\pm 90 days) 
*US Only: Conservative Therapy Sub-study patient follow up evaluations will occur after the primary treatment of anticoagulation is administered at Baseline.
 
(US Only Patients) In addition to the follow-up schedule, approximately 100 patients receiving treatment with the FlowTriever System and approximately 100 patients receiving anticoagulation treatment will be asked to participate in ongoing data collection for 6 months utilizing an Apple iWatch.

Medical Monitor	An independent Medical Monitor will review adverse events and other important safety occurrences as specified in the Safety Manual.
Global Principal Investigator	[name]. Director, Interventional Cardiology Heart and Vascular Institute University of Pittsburgh Medical Center, Pittsburgh, PA

Schedule of Assessments

Assessment	Baseline (\leq 48 hrs.)	Procedure* (Day 0)	48 Hours [†] (\pm 36 hrs.)	30 Days (\pm 15 days)	6 Months (\pm 90 days)
Inclusion/exclusion review	X				
Demographics	X				
Medical History and Risk Factors	X				
Clinical Diagnosis (CTEPH, CTED/Post PE Syndrome)	X			X	X
Current PE Condition	X				
Clinical Condition on Arrival to ED/Hospital	X				
Clinical Condition prior to treatment administration	X				
Anticoagulation regimen	X	X	X	X	X
Clinical Labs: HGB, CBC, Troponin, BNP, Lactate, INR, Creatinine, D-Dimer	X	X	X		
Echocardiogram (Required)	X			X	X
CTPA (Requested) [†]	X				
MMRC Dyspnea Score (Required)	X		X	X	X
Thrombectomy Time		X			
Vitals	X		X	X	X
Invasive hemodynamic measures with HGB, Svo2% (Required)		2X ^Δ			
Pulmonary angiograms		2X			
Bleeding measures		X	X		
FlowTriever Devices used		X			
Access Site information		X			
Procedure Summary (e.g. treatment location, EBL, Fluoro time, clot removal score, HR, pressures)		X			

Adjunctive therapy (thrombolysis and/or additional thrombectomy)	X**	X		X	
6-minute walk test (Required)				X	X
PEmb QOL (Required)				X	X

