7.5 FOLLOW-UP ASSESSMENTS AND WINDOWS

Follow-up evaluation will be scheduled at 48 hours (± 36 hours), 30 days (± 15 days), and 6 months (± 90 days) post-procedure (or post anticoagulation administration for patients enrolled in the Conservative Therapy Sub-study).

The following assessments and procedures will be performed at the 48-hour visit:

- Vitals
- Dyspnea mMRC
- Clinical Labs: HGB, CBC, Troponin, BNP, Lactate, INR, Creatinine, D-Dimer
- Anticoagulation regimen
- Bleeding Measures
- AE observations that occurred since the last visit

The following assessments and procedures will be performed at the 30-day and 6-month visits:

- Vitals
- Clinical Diagnosis (CTEPH, CTED/Post PE Syndrome)
- Echocardiogram
- Dyspnea mMRC
- Anticoagulation regimen
- 6-Minute Walk Test
- PEmb QOL
- AE observations that occurred since the last visit

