7.7 WITHDRAWALS AND LOST TO FOLLOW-UP

Participation is completely voluntary, and each patient is free to withdraw from the study at any time. An investigator also has the right to withdraw the patient from the study in the event of reasons concerning the health or well-being of the patient, or in the case of lack of cooperation. Should a patient decide to withdraw for any reason, or should the investigator decide to withdraw the patient, all efforts will be made to complete and report the observations up to the time of withdrawal as thoroughly as possible. A complete final evaluation at the time of the patient's withdrawal must be made and an explanation given as to why the patient is withdrawing or being withdrawn from the study.

The reason for, and date of, withdrawal must be recorded on the patient's Study Exit CRF. If the reason for the withdrawal is a device-related or procedure-related AE, the event must be reported to the Sponsor and recorded in the CRF.

If the FlowTriever procedure is aborted after entering the vasculature, the patient does not need to complete the follow-up assessments, however, patients who require conversion to open surgery due to incomplete FlowTriever

procedure will be followed for safety through 30 days, or until any treatment-related adverse events resolve, whichever is later. Then the patient will be exited from the study.

All efforts will be made to return patients for all follow-up visits. Due diligence in reaching the patient must be made by two documented telephone contact attempts, emails, or regular postal mail letters. After the above attempts are made, if no response is obtained, the final evaluation of the patient and study exit will be dated on the last visit at which study-related assessments were performed. The Study Exit CRF page will be completed, and communication attempts will be documented.

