2.1. Primary Safety Endpoints

The primary endpoint is the rate of Major Adverse Events (MAE). MAEs are defined as a composite, when one or more of the following events occur:

- Device-related mortality through 48 hours after the index procedure
- Major bleeding through 48 hours after the index procedure
- Intraprocedure device- or procedure-related adverse events (AEs), including:
 - Clinical deterioration defined by hemodynamic or respiratory worsening, or
 - Device-related pulmonary vascular injury, or
 - Device-related cardiac injury

PROPRIETARY AND CONFIDENTIAL

The information contained in this document is the sole property of Inari Medical

	FLASH STATISTICAL ANALYSIS PLAN	Rev. 3.0 Page 5 of 7
---	--	-------------------------

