2.2.1. Secondary Safety Endpoints

- Individual components of the MAE composite endpoint
 - Device-related death through 48 hours after the index procedure
 - Major bleeding through 48 hours after the index procedure, summarized by commonly used scales and each individual element of each scale
 - Clinical deterioration defined by hemodynamic or respiratory worsening
 - Device-related pulmonary vascular injury
 - Device-related cardiac injury
- Major access site complications requiring open surgical or endovascular intervention or blood transfusion
- All-cause mortality within 30 days
- Device-related serious AEs within 30 days

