3.0 ANALYSIS POPULATION

3.1. Full Analysis Population

Up to 1000 patients enrolled in the FLASH registry.

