4.0 INCOMPLETE DATE HANDLING AND MISSING DATA

Incomplete dates will follow the following imputation assignment rules:

1. If day is missing but month and year are present, the day will be set to the first date of the month.
2. If both day and month are missing, but year is present, then January 1st will be used as imputed value.
3. If year is missing, then the date is considered missing.

In general, complete case analysis will be used to handle missing values and no other missing data points other than dates will be imputed.

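### Patients whose procedure is aborted after vascular entry, and who are not converted to open surgery, stay in the analysis set but have no scheduled 48-hour bleeding or 30-day safety check

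*Protocol*

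**What the plan says.** **Who is analysed.** The protocol synopsis (Analytic Datasets) reads "The analytic dataset will comprise all patients enrolled, where enrollment is defined when the FlowTriever System enters" the vasculature, together with consent. Protocol 6.3 defines enrolment the same way and does not ask for a completed thrombectomy. SAP 3.1 defines the Full Analysis Population as "Up to 1000 patients enrolled in the FLASH registry", with no exclusion for aborted cases. Protocol section 6 speaks more loosely of patients treated with the device, but it excludes nobody by name.

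**Who is followed.** Protocol 7.7 states: "If the FlowTriever procedure is aborted after entering the vasculature, the patient does not need to complete the follow-up assessments". The same sentence makes an exception for "patients who require conversion to open surgery" because the procedure was incomplete. They are followed for safety through 30 days, or longer if treatment-related events are unresolved.

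**What the visits supply.** Under Protocol 7.5 the 48-hour visit collects bleeding measures, haemoglobin and "AE observations that occurred since the last visit". The 30-day visit collects adverse events again. These feed "Major bleeding through 48 hours after the index procedure" in the primary composite (SAP 2.1) and "All-cause mortality within 30 days" (SAP 2.2.1).

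**Missing data.** SAP 4.0 says that in general "complete case analysis will be used to handle missing values", with nothing imputed except dates. It has no rule for how excused patients enter the denominators.

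**The concern.** The protocol itself creates this missingness and ties it to failure of the procedure. A case stopped for deterioration, bleeding or failed access is plausibly one where early harm is more likely. If such patients have no scheduled check, a later death or bleed enters the data only when the site happens to hear of it. Complete-case analysis then either omits the patient or, if the absence of a report is read as no event, counts the patient as event-free. Both routes lower the reported rate relative to all enrolled patients, and both favour the device.

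The contact attempts described later in 7.7 are aimed at patients who are due for visits, which these patients are not. Protocol 7.1 and 11.3 record missed required assessments as deviations. An excused assessment need not count as missed, so the gap may leave no trace in the deviation log.

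What is at stake is chiefly the 30-day all-cause mortality rate, and to a lesser degree the 48-hour bleeding and device-related death components of the major adverse event (MAE) rate.

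**Working it through.** FLASH states no target rate, power or precision, so it has no figure of its own to reproduce. The check is first textual, then a small illustration.

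**Step 1: which outcomes lose scheduled ascertainment in an excused patient?**

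| Outcome | Where collected | Status |
|---|---|---|
| Clinical deterioration, pulmonary vascular injury, cardiac injury | At the procedure or within 30 minutes of catheter removal (Protocol 15) | Still captured |
| Major bleeding on the procedure day | Procedure-day bleeding measures (Protocol 7.1, 7.3) | Still captured |
| Later bleeding and device-related death to 48 hours | 48-hour visit (7.5) | Visit excused; reportable if known (9.2) |
| All-cause death to 30 days | 30-day visit (7.5) | Visit excused; reportable if known (9.2) |

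The last two rows are the gap. Protocol 9.2 creates a duty to report but no active vital-status check.

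**Step 2: how large could the effect on 30-day mortality be?**

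Inputs:
- N = 1000, the planned maximum (Protocol 10.1).
- a = number aborted and not converted to open surgery. The documents give no figure; 10, 20 and 30 (1–3%) are assumed.
- Mortality in all other patients = 1%, assumed.
- Mortality in excused patients = 5%, assumed, with no death reported.

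True rate = [(N − a) × 0.01 + a × 0.05] / N

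- a = 10: (9.9 + 0.5) / 1000 = 1.04%
- a = 20: (9.8 + 1.0) / 1000 = 1.08%
- a = 30: (9.7 + 1.5) / 1000 = 1.12%

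Complete-case rate with no excused patient observed = (N − a) × 0.01 / (N − a) = 1.00% in each case. The understatement is 0.04 to 0.12 percentage points. If excused patients are instead counted as alive, the reported rate is 9.9, 9.8 or 9.7 per 1000, that is 0.99%, 0.98% or 0.97%.

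**Step 3: how far does this depend on reporting?**

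If sites report half of the excused deaths and the other excused patients remain unknown, the a = 30 case gives (9.7 + 0.75) / (970 + 0.75) = 1.08% against a true 1.12%. If every death is reported, it gives (9.7 + 1.5) / (970 + 1.5) = 1.15%. That is slightly above the truth, because the deaths are counted but the unknown survivors are not.

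**The case against.** **Ascertainment continues without the visits.** Protocol 9.2 makes major bleeding, device- or procedure-related events and any death reportable regardless of visit attendance. Protocol 7.4 says bleeding is measured for 48 hours and names no exception for aborted cases. Protocol 7.7 waives a requirement; it does not bar data collection. All of this stands, and it is why the gap is passive ascertainment and not absent data. It does not close the gap, because nothing prompts the site to look.

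**The registry is descriptive.** It tests no hypothesis (Protocol 10.2), so no decision turns on this. The illustrated shift of 0.04–0.12 points is also well inside the sampling half-width for 1% of 1000, 1.96 × √(0.01 × 0.99 / 1000) = 0.62 points. That stands too and limits the weight of the point. A systematic shift is nevertheless not random error, and these rates are the registry's main safety output.

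**Stronger readings that a reader might infer.**
- *That the primary endpoint goes uncollected in these patients.* It does not: three of its five components are intraprocedural, and procedure-day bleeding is recorded.
- *That excused patients die at the 25% quoted as the low end for massive PE in Protocol 1.4*, giving 1.24–1.72% over the same abort range. The registry also enrols intermediate-risk patients, and nothing in the documents gives that mortality for aborted cases.
- *That all 20 of 20 excused patients could have died*, giving a rate as high as (9.8 + 20) / 1000 = 2.98%. This is an arithmetic limit that requires every death to go unreported.
- *That the MAE rate is materially wrong.* Taking FLARE's 3.8% for followed patients and unseen bleeding in 10% of 10 to 30% of 30 excused patients gives 0.99 × 3.8% + 0.01 × 10% = 3.9% to 0.97 × 3.8% + 0.03 × 30% = 4.6%. The documents support none of those bleeding rates.
- *That every patient moved to lysis or another device is excused.* The protocol does not define an aborted procedure, and adjunctive therapy is recorded as procedure data.

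**Conclusion.** The point holds in a limited form. Enrolled patients with an aborted, non-converted procedure belong to the analysis set but are excused from the scheduled checks that would find later bleeding and death, and the SAP does not say how they are counted. The main exposure is 30-day all-cause mortality. Post-procedure bleeding and device-related death to 48 hours come second.

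Under the stated assumptions the understatement is about 0.1 percentage point or less. It is zero if sites report every death, and larger only under abort or mortality rates that the documents do not give. The size is therefore uncertain and probably small. The direction, when events go unreported, favours the device. The change is worth making because it is cheap and because the sponsor already provides 30-day safety follow-up after conversion to surgery.

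**What to change.** **Protocol 7.7.** Replace the waiver with a rule along these lines: when a procedure is aborted after the FlowTriever has entered the vasculature, the patient stays enrolled, has a 48-hour bleeding and AE assessment, and has a 30-day vital-status and AE check by visit, telephone or chart review. Echocardiogram, 6-minute walk, mMRC and PEmb-QOL are waived. The existing follow-up for open-surgery conversions is kept.

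**SAP 3.1.** State that aborted procedures are in the Full Analysis Population. This also settles the looser wording in Protocol section 6.

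**SAP 5.2.** Report the number of aborted procedures and the number of patients with unknown 48-hour and 30-day status, and show the denominator beside each rate.

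**Cost.** Wording in two documents and one call or chart check per aborted patient, about 10–30 patients under the assumed abort rate. Patients who have already exited may remain unknown, and the reported count will show how many. Reported event rates may rise slightly.

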7.8 COVID-19 EFFECT ON RESEARCH

This Registry study was designed to capture real-world data regarding the clinical use of the FlowTriever System (and anticoagulation treatment in the Conservative Therapy Sub-study). As a result of the COVID-19 pandemic, clinic practice patterns may have been affected and patient visits may have been postponed or eliminated. In addition, some data may be collected from patients over the phone. Our goal is to collect as much real-world data as possible while protecting everyone's safety.

8 RISK ANALYSIS

8.1 RISKS TO PATIENTS

The FLASH Registry involves the use and disclosure of deidentified health information. It collects only information relevant to the patient's PE condition and treatment.

The Registry study involves the collection of specific information for research and educational purposes only. It does not specify how the FlowTriever System or anticoagulation will be used to treat PE, and decisions regarding a patient's treatment are not influenced by the Registry study. Physicians participating in the Registry study are expected to review the indications, contraindications, warnings, precautions, and safety events described in the IFUs. As with any endovascular procedure or anticoagulation regimen, the treating physician is expected to counsel the patient on the risks and benefits specific to the planned treatment and to obtain the local, procedure-related, or treatment-related informed consent per institutional policies and procedures.

8.2 RISK MITIGATION

The Registry study was designed to capture real world data regarding the clinical use of the FlowTriever System (and anticoagulation treatment in the US Conservative Therapy Sub-study). The risks of providing this personal health information have been mitigated, as no personal information directly identifying the patient will not be collected for the Registry database. At the time of participation, each participant will be assigned a unique study identification number. This number will be used in the database to identify the patient. All data handling will be in accordance with GDPR and HIPAA requirements and only de-identified information will be entered.

9 SAFETY ASSESSMENT

9.1 DEFINING ADVERSE EVENTS

An AE is any untoward medical occurrence or exacerbation of an existing medical condition subsequent to treatment with the FlowTriever. AEs are classified in several ways, including severity, relationship, and seriousness.

- Severity (mild, moderate, severe)

- **Mild:** No limitation of usual activities, no therapy or only symptomatic therapy required to treat the injury or illness.
- **Moderate:** Some limitation of usual activities or specific therapy is required.
- **Severe:** Inability to carry out usual activities, hospitalization, emergency treatment, life-threatening events, or mortality.
- Relationships (unrelated, device-related, procedure-related, drug-related, or relationship unknown) are defined below.

Unrelated: The clinical event is completely independent of study procedure/study device and/or evidence exists that the event is definitely related to another etiology.

Device-related: The event is directly related to the study device itself, as defined by its intended use. AEs will be considered unrelated to the device if the complication could have occurred if the device functioned entirely within its specifications.

Procedure-related: Procedure-related events include all AEs that occur at any time of patient participation that was directly related to the procedure. The exception to this rule is an event that is device-related; such events should not also be classified as procedure-related.

Drug-related: Event is attributable to thrombolytic or anticoagulant therapy. These events may occur from inadequate (thrombosis) or excessive therapy (bleeding). A drug-related AE cannot also be classified as device-related, but many will be classified as procedure-related, since the drug may be part and parcel of the index procedure or the event may have occurred within 30 days.

Relationship unknown: The relationship to the study procedure/study device is not known.

A **Serious Adverse Event (SAE)** is an event that meets at least one of the following:

- Is fatal
- Is life-threatening
- Results in persistent or significant disability/incapacity
- Results in permanent impairment of a body function or permanent damage to a body structure
- Results in hospitalization or prolongs a hospitalization
- Necessitates medical or surgical intervention to preclude permanent impairment of a body function or permanent damage to a body structure
- Results in a congenital anomaly or birth defect
- Serious deterioration of the health of the patient that resulted in chronic disease

9.2 REPORTING OF EVENTS

The FLASH Registry study was designed to capture real-world data regarding the clinical use of the FlowTriever System (and anticoagulation treatment in the Conservative Therapy Sub-study) and involves the collection of specific information for research and educational purposes only. It does not specify how the FlowTriever System or anticoagulation will be used to treat PE, and decisions regarding a patient's treatment are not influenced by the study. This is a data collection study only; there is nothing investigational or experimental in the patient's medical treatment.

Therefore, the study will only capture AEs related to the patient's PE condition and its treatment. Reportable AEs include all events considered in the safety analyses (e.g., major bleeding^c), all device- and/or procedure-related AEs, as well as any event resulting in mortality.

The AEs will be captured on the Adverse Event CRF and should include, wherever possible, severity, duration, outcome, the Investigator's description of the event, and his/her medical judgment as to the relationship of the AE (i.e., not related, related, or relationship unknown) to the study device, to the index procedure or any subsequent procedure(s), to a thrombolytic agent or anticoagulant, or underlying disease.

- Non-serious reportable AEs are to be submitted via the electronic data capture system (EDC) in a timely fashion.
- Reportable SAEs must be reported to the Sponsor within 5 business days of the Investigator's knowledge of the event. The event is reported in the EDC.

Appendix 1 includes a list of possible SAEs associated with thrombectomy, including those events considered major device-related events and major morbidity. These events are considered reportable at all time points throughout the study and require submission to the Sponsor and the IRB/EC and regulatory authorities, as required.

10 STATISTICS & DATA ANALYSIS

10.1 SAMPLE SIZE

The sample size of up to 1000 patients (up to 800 US and up to 200 Europe) for the FlowTreiver System and up to an additional 300 patients for anticoagulation treatment reflects an adequate size to accrue data on real-world use, as assessed in up to 100 (up to 70 US, up to 30 Europe) registry sites.

10.2 STATISTICAL METHODOLOGY

This is an observational study and as such is not hypothesis-driven. The endpoints will be assessed for patients receiving treatment with the FlowTriever System with descriptive statistics. Continuous variables will report any combination of mean, median, Q1, Q3, IQR, minimum and maximum while the categorical variables will report frequency count and percentages (%). Additional ad-hoc and exploratory analyses for both the main study and US Conservative Therapy Sub-study will be separately defined in the Statistical Analysis Plans.

11 STUDY MANAGEMENT CONSIDERATIONS

11.1 DATA MANAGEMENT AND COLLECTION OF CLINICAL DATA

The Sponsor and/or designee will be responsible for the processing and quality control of the data. All source data, CRFs, copies of protocols and protocol amendments, correspondence, patient identification lists, informed consent forms, and other essential documents must be retained for a period of at least 2 years after study completion or closure.

No study document or image will be destroyed without prior written agreement between the Sponsor and the Investigator prior to the conclusion of the retention period. Should the Investigator wish to assign the study records to another party or move them to another location, advance written notice must be given to the Sponsor.

^c For the purposes of this study, mild to moderate pain or ecchymosis at the access site do not require reporting as adverse events.

